### 10.4.3 Analysis of the secondary efficacy endpoints

Progression-free survival (PFS) will be determined using the Kaplan-Meier method, considering those who progress or die without progression as failures, and censoring those who do not.

Overall survival (OS) will be determined using the Kaplan-Meier method.

Each of these will be calculated starting from the date the patient enrolled onto the trial. Appropriate confidence intervals will be reported for each of these measures.

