Despite altering the prognostic landscape for a subset of patients with limited and toxic treatment options, many patients fail to respond to upfront therapy with immune checkpoint blockade and additional subsets of patients ultimately develop acquired resistance to this approach. To underscore this point, objective response rates in the second-line UC setting range from 15-21% with modestly higher response rates in the upfront UC setting (23.5-24%). As shown by Keynote-45 PD-1/PD-L1 check point blockade can have a durable response in metastatic urothelial patients. When compared to chemotherapy in the second line setting patients receiving pembrolizumab had an overall survival of 10.3 months (95% confidence interval [CI], 8.0 to 11.8) compared with 7.4 months (95% CI, 6.1 to 8.3). Novel combination strategies are needed to extend the benefit of immunotherapy to the remaining 75-85% of non-responders with metastatic non-prostate genitourinary cancer [8]. This population represents a clear unmet clinical need as these patients continue to succumb to rapid and lethal progression of disease despite currently approved therapies.

[figure not shown]

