### 2.2.2 Screening activities performed after a consent for screening has been signed

Screening evaluation testing/procedures are conducted under the separate screening protocol, 01-C-0129 (Eligibility Screening and Tissue Procurement for the NIH Intramural Research Program Clinical Protocols). Assessments performed at outside facilities or on another NIH protocol within the timeframes below may also be used to determine eligibility once a patient has signed the consent.

All screening tests and procedures must be performed within 21 days prior to initiation of study therapy except physical exam with skin assessment, ECOG, vital signs, blood tests and pregnancy test (repeated if >7 days):

- Complete medical history and physical examination (including height, weight, vital signs, and ECOG performance status) and skin assessment.
- Electrocardiogram (ECG)
- CT scan of chest, abdomen and pelvis with IV and PO (as indicated) contrast, or CT chest and MRI abdomen/pelvis may be performed, and [18F]-Sodium Fluoride (NaF) PET/CT bone scan (if indicated).
- Laboratory assessments: CBC with differential, acute care panel (sodium, potassium, chloride, total CO2 (Bicarbonate), creatinine, glucose, urea nitrogen), mineral panel (albumin, calcium total, magnesium total, phosphorus), hepatic panel (alkaline phosphatase, ALT/GPT, AST/GOT, total bilirubin, direct bilirubin), ionized calcium, amylase, lipase, LDH, total protein, GGT, Hepatitis B and C, PT/INR, PTT, urine analysis.
- Hepatitis B and C antibody panel
- Thyroid function tests – TSH, reflex T3 and T4
- Pre-treatment tissue biopsy and/or archival tissue availability for PD-L1 expression retrospective testing is mandatory for enrollment. PD-L1 will be performed retrospectively by EMD Serono using a test determined by EMD Serono.
- Pregnancy test for females of childbearing-potential (within 3 days prior to first dose of study drug).
- Lymphocyte Phenotyping - CD4/CD8 will be performed on known HIV-positive patients.

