#### 6.3.3.3 Evaluation of Best Overall Response

The best overall response is the best response recorded from the start of the treatment until disease progression/recurrence (taking as reference for progressive disease the smallest measurements recorded since the treatment started). The patient's best response assignment will depend on the achievement of both measurement and confirmation criteria.

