**6.3.4 Duration of Response**

Duration of overall response: The duration of overall response is measured from the time measurement criteria are met for CR or PR (whichever is first recorded) until the first date that recurrent or progressive disease is objectively documented (taking as reference for progressive disease the smallest measurements recorded since the treatment started).

The duration of overall CR is measured from the time measurement criteria are first met for CR until the first date that progressive disease is objectively documented.

Duration of stable disease: Stable disease is measured from the start of the treatment until the criteria for progression are met, taking as reference the smallest measurements recorded since the treatment started, including the baseline measurements.

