**6.3.5 Progression-Free Survival**

PFS will be defined as the duration of time from start of treatment to time of progression or death, whichever occurs first.

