**10.3 POPULATIONS FOR ANALYSES**

Modified intention to treat: all patients who receive at least one dose of each agent will be included in the statistical analyses performed.

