### 10.4.6 Sub-Group Analyses

Analyses will be performed by arm without further sub-analyses.

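### PFS starts at first treatment in section 6.3.5 but at enrollment in section 10.4.3, the enrollment clock does not fit the dosed-only analysis set, and no analysis unit is named for PFS and OS

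*Combined protocol and SAP*

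**What the plan says.** **Start date.** Section 6.3.5 states: "PFS will be defined as the duration of time from start of treatment to time of progression or death, whichever occurs first". Section 10.4.3, after assigning Kaplan-Meier estimation to PFS and OS, states: "Each of these will be calculated starting from the date the patient enrolled onto the trial". That sentence is the only place where an origin for OS is given.

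Elsewhere section 6.3 counts from treatment. Section 6.3.3.3 says: "The best overall response is the best response recorded from the start of the treatment until disease progression/recurrence". Section 6.3.4 says: "Stable disease is measured from the start of the treatment until the criteria for progression are met".

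**Who is analysed.** Section 10.3 defines a modified intention-to-treat set: "all patients who receive at least one dose of each agent will be included in the statistical analyses performed".

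**Unit of analysis.** Section 10.4.2 reports the response rate cohort by cohort, and section 10.4.5 runs the interim look within each cohort. Section 10.4.3 names no unit. Section 10.4.6 says: "Analyses will be performed by arm without further sub-analyses". Section 2.3.1 defines a single Arm 1 and assigns all four cohorts to it. The secondary objective (1.1.2) and secondary endpoint (10.1.2) mention no cohort.

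**Evaluation interval.** Section 6.3 moves to 12-weekly response evaluation after one year. Appendix A, footnote 8, keeps scans 8-weekly until progression or a new anti-cancer treatment.

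**The concern.** One protocol should not give PFS two starting points. As it stands, either origin can be defended from the text, and the choice could be made after the data are seen.

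The enrollment origin also sits badly with the dosed-only set. A patient who enrolls and dies before treatment is left out, while everyone who is kept is alive at first dose by construction. Time between enrollment and first dose therefore lengthens PFS and OS, or leaves them unchanged; it cannot shorten them.

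This is a single-arm trial, so its PFS and OS will be read against outside figures such as those cited in section 1.2.1. Origin and population then decide what the reported number means. If section 10.4.6 were applied to the letter, there would also be one PFS curve and one OS curve mixing checkpoint-naive with previously treated patients, whom the plan otherwise treats as separate populations with different null response rates (15%, 10%, 5% and 5% in section 10.2).

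**Working it through.** The plan gives no sample size, event count or precision figure for PFS or OS, so there is no stated number to reproduce. The check compares the texts and then scales the possible effect.

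**1. The two origins.** For any analysed patient:

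- PFS under 10.4.3 = PFS under 6.3.5 + (date of first dose − date of enrollment).
- OS under 10.4.3 = OS from first dose + the same gap.

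Example: progression at the first 8-week scan, 56 days after first dose, with an assumed 14-day gap. Section 6.3.5 gives 56 days; section 10.4.3 gives 56 + 14 = 70 days.

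**2. Size of the gap.** No section states the enrollment-to-dose interval. The nearest guide is section 2.2.2: "All screening tests and procedures must be performed within 21 days prior to initiation of study therapy". The same sentence excepts some assessments, which are repeated if more than 7 days old. This is a window for tests, not a limit on the gap, so 0 to 21 days is an assumption. Converting with 30.44 days per month:

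| Assumed gap | Added to PFS and OS |
|---|---|
| 0 days | 0 |
| 7 days | 7/30.44 = 0.23 month |
| 14 days | 14/30.44 = 0.46 month |
| 21 days | 21/30.44 = 0.69 month |

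For scale only, section 1.2.1 reports of a second-line trial that "patients receiving pembrolizumab had an overall survival of 10.3 months". Against that, 0.69/10.3 = 6.7%. The 21 days is not a firm cap. Section 6.3.2 lets baseline tumor evaluation be up to 4 weeks before treatment, and a 28-day gap would add 28/30.44 = 0.92 month.

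**3. Direction.** Section 10.3 requires at least one dose, so the chance that an analysed patient dies inside the gap is zero. The gap is guaranteed-alive time in both endpoints.

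**4. Analysis unit.** By arm (10.4.6) plus one arm (2.3.1) literally gives one pooled curve per endpoint. By cohort for response (10.4.2) and for the interim (10.4.5), together with section 3.1 referring to all arms in a one-arm trial, suggests that arm is used loosely for cohort.

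**5. Precision by cohort.** Approximate 95% half-width at a survival fraction of 0.5 without censoring is 1.96 × √(0.25/n):

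| n | Half-width (percentage points) |
|---|---|
| 15 (full 1B) | 25.3 |
| 16 (full 1A, 2A) | 24.5 |
| 21 (full 2B) | 21.4 |
| 68 (pooled) | 11.9 |
| 8 to 12 (cohort stopped at stage 1) | 34.6 to 28.3 |

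**6. Evaluation interval.** If progression onset is uniform between scans, mean detection delay is half the interval: 8/2 = 4 weeks or 12/2 = 6 weeks. The 2-week difference applies only to patients still progression-free at one year.

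**The case against.** **OS is not contradictory.** A reader might infer that both endpoints have conflicting definitions. They do not: OS has one origin, enrollment. The objection to it is the mismatch with the dosed-only set, not a contradiction. This stands, and the point on OS is limited accordingly.

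**The gap may be nothing.** A reader might infer that reported PFS is bound to differ or is materially inflated. The documents do not support that, because the interval is not given and may be zero. Analysts could differ; it is not certain that they would. The month figures are assumed values, and the comparison median belongs to a different drug's trial.

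**Other intervals counted from treatment add little.** Best overall response is a window for choosing a response, and duration of stable disease is not among the endpoints analysed in section 10.4. They show that section 6.3 consistently counts from treatment, but they affect no planned analysis.

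**By cohort is probably intended.** A reader might infer that the plan means to pool PFS and OS over all cohorts. The heading of 10.4.6 and the wording of 10.4.2, 10.4.5 and 3.1 point the other way, so calculations of the mix in a pooled curve would quantify an unlikely reading. What remains is a missing phrase in 10.4.3 and a wrong word in 10.4.6.

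**Another repair is coherent.** An enrollment origin with all enrolled patients analysed would also be consistent, but section 10.3 does not adopt that set.

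**These are descriptive secondary endpoints.** True, and this limits the weight of the point. It does not remove the conflict between 6.3.5 and 10.4.3.

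**Conclusion.** The PFS conflict is established by the text alone and needs no assumption. The enrollment clock is also mismatched to the dosed-only set for both PFS and OS. Its direction is certain (longer or unchanged); its size is not documented. It is zero with same-day dosing and 0.23 to 0.69 month under an assumed gap of 7 to 21 days.

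The unit of analysis for PFS and OS is unstated in 10.4.3 and wrong as worded in 10.4.6, although the intention is probably by cohort. The 8-weekly versus 12-weekly discrepancy is real but separate and minor.

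These points should be corrected before PFS or OS is analysed. A reader might fear that the trial's go/no-go decisions are affected; they are not, because those rest on objective response by cohort, which uses neither the PFS/OS clock nor a pooled curve.

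**What to change.** - **Sections 6.3.5 and 10.4.3:** state the date of first dose as the single origin for both PFS and OS, in the same words. This keeps 6.3.5 as it is in substance and matches the set in 10.3. If the sponsor prefers enrollment, the analysis set for these endpoints would have to become all enrolled patients.
- **Section 10.4.3:** add that PFS and OS are estimated separately by cohort (1A, 1B, 2A, 2B).
- **Section 10.4.6:** change arm to cohort, and label any curve pooled over cohorts as supplementary.
- **Section 6.3 and Appendix A, footnote 8:** reconcile the evaluation interval after one year.

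The cost is wording. Sample size, response rules and stopping boundaries do not change. By-cohort intervals are wider than pooled ones: about ±21 to ±25 points for full cohorts against ±12 pooled, and about ±28 to ±35 for a cohort stopped at its first stage.

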### 10.4.4 Baseline Descriptive Statistics

Demographic and baseline clinical characteristics of all patients will be reported.

### 10.4.5 Planned Interim Analyses

As indicated above, for each phase II cohort, using a Simon two-stage design, after the required number of evaluable patients have been enrolled in the first stage, an analysis of the response rate will be undertaken to determine if there are sufficient responses to proceed to the second stage.

### 10.4.6 Sub-Group Analyses

Analyses will be performed by arm without further sub-analyses.

### 10.4.7 Tabulation of Individual Participant Data

None will be provided.

### 10.4.8 Exploratory Analyses

1. Determine peripheral immune modulation using:
  - Multi-parametric flow cytometry – immune subset analysis
  - Cytokine/chemokine analysis (i.e TGF- $\alpha$ , IFN- $\gamma$ , IL-6, IL-8, etc.)
  - Blood-based immune parameters (neutrophil-to-lymphocyte ratio)
  - Circulating Tumor Cells (CTCs) and circulating cell-free tumor DNA (cfDNA)
2. Determine immune status of the tumor microenvironment using:
  - Multiplex IHC for PD-L1 expression, CD8, CD4, FoxP3 T-cell infiltration
  - RNA-Seq transcriptome sequencing for tumor/immune gene expression profile (and peripheral blood mononuclear cells)
  - T-cell receptor (TCR) sequencing for T-cell clonality and MET protein levels
  - Next generation sequencing (TSO-500) for tumor biomarkers in tumor samples

Any of these exploratory evaluations which generate quantitative measures will be done using descriptive statistics including confidence intervals when appropriate. Any statistical tests performed for evaluation of exploratory objectives will be done without formal adjustment for multiple comparisons, but in the context of the number of tests performed.

## **11 COLLABORATIVE AGREEMENTS**

### **11.1 CRADA**

This study will receive the investigational study agent under a Cooperative Research and Development Agreement (CRADA) with EMD Serono. CRADA Number: 02666.

## **12 HUMAN SUBJECTS PROTECTIONS**

### **12.1 RATIONALE FOR SUBJECT SELECTION**

Cisplatin ineligible or platinum refractory metastatic urothelial cancer patients may have received prior checkpoint inhibitor therapy or be checkpoint inhibitor naïve to enroll. Patients with metastatic urothelial cancer who received prior checkpoint inhibitors are left with limited options and the effect of subsequent immunotherapy treatment is unknown. While current PD-1/PD-L1 checkpoint inhibitors have shown efficacy in checkpoint naïve patients who are either cisplatin ineligible or refractory response rates are about 20% [46]. Therefore, it is imperative to improve on this response rate with drugs like M7824 that have potential of increasing response rates through immunomodulation. These reasons express the need to determine M7824 activity in our patient population.

Participants who do not accept blood transfusions will be excluded. As there is a risk of severe bleeding with this study drug, participants must be willing to receive blood transfusions if medically necessary for their own safety. Participants must be able to receive blood transfusions in order to minimize the risks of receiving M7824. Another reason for this is that including these patients could compromise the scientific validity of the study. For example, death from blood loss could make it difficult to assess other aspects of the investigational immunotherapy's safety—a primary scientific goal in this early-phase immunotherapy trial, which are carried out in small numbers of participants.

### **12.2 PARTICIPATION OF CHILDREN**

Because no dosing or adverse event data are currently available on the use of M7824 in patients less than 18 years of age, children are excluded from this study.

### **12.3 PARTICIPATION OF SUBJECTS UNABLE TO GIVE CONSENT**

Adults unable to give consent are excluded from enrolling in the protocol. However, it is possible that subjects enrolled in the protocol may permanently lose the capacity to consent for themselves during the course of this study. In the event this occurs, the subjects will remain in the study because there is a prospect of direct benefit (Section 12.5.2) from research participation. All subjects  $\geq$  age 18 will be offered the opportunity to fill in their wishes for research and care, and assign a substitute decision maker on the “NIH Advance Directive for Health Care and Medical Research Participation” form so that another person can make decisions about their medical care

in the event that they become incapacitated or cognitively impaired during the course of the study. Note: The PI or AI will contact the NIH Ability to Consent Assessment Team (ACAT) for evaluation to assess ongoing capacity of the subjects and to identify an LAR, as needed.

Please see Section **12.6.1** for consent procedure.

## **12.4 EVALUATION OF BENEFITS AND RISKS/DISCOMFORTS**

Patients will receive evaluation of their disease at the National Cancer Institute's Clinical Center.

Potential adverse reactions attributable to the administration of the study drug utilized in this trial are discussed in Section **14**. All care will be taken to minimize side effects, but they can be unpredictable in nature and severity. Patients will be examined and evaluated prior to enrollment. All evaluations to monitor the treatment of patients will be recorded in the patient chart. If patients suffer any physical injury as a result of the participation in this study, immediate medical treatment is available at the Clinical Center, National Cancer Institute, Bethesda, Maryland.

The potential benefit to a patient that goes onto study is a reduction in the bulk of their tumor which may or may not have favorable impact on symptoms and/or survival.

Although no compensation is available, any injury will be evaluated and treated in keeping with the benefits or care to which patients are entitled under applicable regulations. In all publications and presentations resulting from this trial, patients' anonymity will be protected to the maximum extent possible. Authorized personnel from the National Cancer Institute (NCI) and Food and Drug Administration (FDA) or other regulatory authorities may have access to research files in order to verify that patients' rights have been safeguarded. In addition, patient names will be given to the Central Registration to register patients onto the study.

## **12.5 RISKS/BENEFITS ASSESSMENT**

### **12.5.1 Known Potential Risks**

The primary risk to patients participating in this research study is the potential toxicity of the M7824. Potential adverse reactions attributable to the administration of the study drug utilized in this trial are discussed in Section **14.1.2**. The protocol provides detailed and careful monitoring of all patients to assess for toxicity. Toxicity data will be collected and reviewed to ensure that there were no severe toxicities that would preclude further patient enrollment. Patients will be treated with therapeutic intent and response to the therapy will be closely monitored.

#### **12.5.1.1 Blood Sampling**

Side effects of blood draws include pain and bruising, lightheadedness, and rarely, fainting.

#### **12.5.1.2 Electrocardiogram**

Some skin irritation can occur where the ECG/EKG electrodes are placed. The test is completely painless, and generally takes less than a minute to perform.

#### **12.5.1.3 Tumor Biopsy**

Needle biopsy is minimally invasive and is typically a very safe procedure. Depending upon the site being biopsied and the type of biopsy being performed, risks can include infection of the

biopsy site, development of a hematoma, and bleeding. Rarely more significant complications can occur when structures near the biopsy target are entered with the needle (e.g. puncture of lung or bowel). Surgical procedures for biopsy specimens will not be conducted for the sole purpose of research specimen collection, although when surgical biopsies are performed for clinical or NCI protocol requirements, samples may be requested as part of participation on this trial. In this instance, no added risk is incurred.

#### 12.5.1.4 Imaging

In addition to the radiation risks discussed below, CT scans may include the risks of an allergic reaction to the contrast. Participants might experience hives, itching, headache, difficulty breathing, increased heart rate and swelling.

#### 12.5.1.5 MR Imaging

The risks of MR imaging are relatively small. Participants undergoing gadolinium enhanced MRIs may also be at risk for kidney damage. MRIs include the additional risk of damage to hearing.

#### 12.5.1.6 Risks of exposure to ionizing radiation

This research study involves up to 7 CT C/A/P scans and up to 3 CT-guided biopsies. Pre-treatment tissue biopsy and tissue availability is mandatory. On-treatment biopsy is required unless obtaining biopsy is not technically or clinically feasible. Post-treatment biopsy is optional. Subjects will be exposed to up to approximately 10.1 rem.

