## 3 STUDY IMPLEMENTATION

### 3.1 STUDY DESIGN

- This is an open label, non-randomized, single arm phase II trial of M7824 in checkpoint inhibitor naïve and refractory patients with urothelial carcinoma.
- We will plan to use a fixed dose of 1200 mg delivered IV every 2 weeks (Q2W) based on the recent NCI-led phase I dose-escalation trial of M7824 in advanced solid tumors (NCT02517398) [33]. M7824 appeared to have a manageable safety profile and early evidence of clinically efficacy. The MTD was not reached in this study at 20mg/kg and

- PD-L1 receptor occupancy and sequestration of TGF- $\beta$  isoforms 1-3 was achieved at M7284 dose levels >1mg/kg.
- A maximum of 68 evaluable subjects will be enrolled in checkpoint naïve [Cohort 1] and checkpoint inhibitor refractory [Cohort 2] patients with urothelial carcinoma of the bladder.
    - Cohort 1A: Checkpoint inhibitor naïve patients who are cisplatin-ineligible
    - Cohort 1B: Checkpoint inhibitor naïve patients who are refractory post-platinum therapy
    - Cohort 2A: Checkpoint inhibitor refractory patients with Complete Response (CR) or Partial Response (PR) as per RECIST 1.1
    - Cohort 2B: Checkpoint inhibitor refractory patients with Stable Disease (SD) or Progressive Disease (PD) as per RECIST 1.1
  - Enrollment of 2-3 patients per month is expected on this trial; thus, 2 to 3 years is anticipated as the accrual period.
  - Restaging will be performed every 2 cycles (8 weeks). Safety/tolerability analysis and secondary clinical efficacy analysis will be ongoing through cycle 4. Patients can continue study drug in all arms provided there is no confirmed evidence of progression, unacceptable toxicity or withdrawal from the study.

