## **6.3 RESPONSE CRITERIA**

For the purposes of this study, patients should be re-evaluated for response every 8 weeks. After one year response evaluation will be done every 12 weeks. In addition to a baseline scan, confirmatory scans should also be obtained 4-8 weeks (not less than 4 weeks) following initial documentation of objective response.

Response and progression will be evaluated in this study using the new international criteria proposed by the revised Response Evaluation Criteria in Solid Tumors (RECIST) guideline (version 1.1) [45]. Changes in the largest diameter (unidimensional measurement) of the tumor lesions and the shortest diameter in the case of malignant lymph nodes are used in the RECIST criteria.

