8. CT of chest, abdomen and pelvis with IV contrast (oral contrast as indicated) or CT of the chest without contrast and MRI abdomen/pelvis with tumor measurements. For this study patients should be re-evaluated for response every 8 weeks (+/- 10 days). If a scan identifies objective response or progressive disease, a confirmatory scan should be obtained 4-8 weeks following initial documentation of objective response or progression. In patients with clinical progression or unequivocal scan, confirmatory progression scan can be deferred. Scans will continue every 8 weeks until disease progression or start of a new anti-cancer treatment.
9. After disease progression or in those subjects who were removed from study therapy for reasons other than disease progression, subjects will be followed every 12 weeks in clinic or by telephone/email for assessment of survival status, related adverse events and documentation of initiation of new anti-cancer therapy.
10. If appropriate screening imaging is done within 21 days of C1D1 repeat screening imaging is not required.
11. All SAEs ongoing at the 30-day (+/- 10 days) safety follow-up visit must be monitored and followed up by the investigator until stabilization or until the outcome is known, unless the subject is documented as "lost to follow-up." In addition, all trial drug-related SAEs occurring after 30 day safety follow up visit and ongoing at the Safety Follow-up visit have to be followed up in the same manner.
12. Skin assessment must be performed at baseline and at least every 6 weeks during treatment and at the end of treatment or 28 (±5 days) days post-treatment safety follow-up (if not performed in the previous 6 weeks).

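### The stated maximum of 7 CT scans and about 10.1 rem has no time frame, and the protocol's own schedule passes it for patients progression-free beyond week 48

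*Combined protocol and SAP*

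**What the plan says.** Section 12.5.1.6 gives the protocol's radiation figures: "This research study involves up to 7 CT C/A/P scans and up to 3 CT-guided biopsies", and then "Subjects will be exposed to up to approximately 10.1 rem". Both are written as maxima for the study. Neither carries a time frame, and no dose per scan or per biopsy is given.

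The imaging schedule is set elsewhere:

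- Section 2.2.2 requires a CT of chest, abdomen and pelvis at screening, or CT chest with MRI of abdomen and pelvis. It adds an NaF PET/CT bone scan where indicated.
- Section 3.1 restages every two 4-week cycles and sets no limit on treatment: "Patients can continue study drug in all arms provided there is no confirmed evidence of progression, unacceptable toxicity or withdrawal from the study". Section 3.6.1 lists completion of therapy as a reason for removal, but no cycle count defines completion.
- Section 6.3 keeps the 8-week interval for the first year and then says: "After one year response evaluation will be done every 12 weeks".
- Appendix A, footnote 8, does not change the interval at one year: "Scans will continue every 8 weeks until disease progression or start of a new anti-cancer treatment".
- Section 6.3 and footnote 8 ask for a confirmatory scan 4 to 8 weeks after a response is first documented. Footnote 8 asks the same after progression, with exceptions.

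**The concern.** A reader takes a figure introduced by the words up to as a ceiling that no participant will pass. The schedule contains no such ceiling. The protocol plans evaluations beyond one year, so passing 7 scans is an expected result of following the plan, not a deviation from it.

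The figure supports the risk and benefit assessment in section 12.5. If it covers only the first year without saying so, it understates exposure for the patients who stay on study longest.

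**Working it through.** **Reproducing the 7.** Inputs: one screening scan (section 2.2.2) and restaging every 8 weeks (sections 3.1 and 6.3).

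Scans in the first 52 weeks = 1 + floor(52/8) = 1 + 6 = 7, at screening and weeks 8, 16, 24, 32, 40 and 48.

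The stated 7 is exactly the routine first-year count. It leaves no room for an extra scan.

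**Beyond week 48**, for a patient without progression or new anti-cancer therapy:

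| Rule after one year | Eighth visit | Visits by week 104 |
|---|---|---|
| Every 8 weeks (Appendix A, footnote 8) | week 56 | 1 + 104/8 = 14 |
| Every 12 weeks (section 6.3), counted from week 48 | week 60 | 7 + 4 (weeks 60, 72, 84, 96) = 11 |
| Every 12 weeks (section 6.3), counted from week 52 | week 64 | 7 + 4 (weeks 64, 76, 88, 100) = 11 |

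Against the stated 7, this is 11/7 = 1.57 to 14/7 = 2.00, or 57% to 100% more imaging visits at two years.

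**Confirmatory scan.** If a response seen at week 8 is confirmed at week 12, the scans fall at screening and weeks 8, 12, 16, 24, 32, 40 and 48, which is 8 by week 48. If it is confirmed at the next routine scan (week 16), nothing is added.

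**Dose.** The 10.1 rem cannot be reproduced without per-procedure doses. As an assumption, let one CT of chest, abdomen and pelvis give *a* rem and one biopsy *b* rem, with 7*a* + 3*b* = 10.1 and 0 ≤ *b* ≤ *a*.

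- If *b* = 0, then *a* = 10.1/7 = 1.44.
- If *b* = *a*, then *a* = 10.1/10 = 1.01.

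With all three biopsies and a full CT at every visit, *n* scans give 10.1 + (*n* − 7)*a*:

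| Scans | Low (*a* = 1.01) | High (*a* = 1.44) |
|---|---|---|
| 8 | 11.1 rem | 11.5 rem |
| 11 | 14.1 rem | 15.9 rem |
| 14 | 17.2 rem | 20.2 rem |

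**Fewer biopsies.** At *a* = *b* = 1.01, 8 scans with two biopsies give 10 × 1.01 = 10.1 rem, and with one biopsy 9 × 1.01 = 9.1 rem. So an eighth scan does not by itself prove that 10.1 rem is passed. Eleven full CTs with no biopsy give at least 11 × 1.01 = 11.1 rem, which is above 10.1 anywhere in the assumed range. Replacing some scans with CT chest plus MRI would lower all these totals by an amount that the documents do not allow one to calculate.

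**The case against.** The best defence is that 7 is plainly a first-year figure. It matches the 52-week count exactly, so no sum is wrong and only a label is missing. The match is persuasive, but the section describes what the study involves and does not mention a year. As written, it asserts a maximum that the schedule exceeds.

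Several stronger readings are tempting, and the documents do not support them:

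- *All responders exceed the figure.* They do not. A responder who progresses by week 48, with any confirmatory scan falling on a routine visit, can stay at 7 or below. A patient with long stable disease can exceed it without responding. The affected group is patients progression-free beyond week 48, plus those with off-schedule confirmatory scans.
- *The end-of-treatment visit adds a CT.* The calendar's columns do not line up reliably in the text available. The last CT mark sits in the same position as the last dosing mark, so an end-of-treatment CT is not established.
- *The 10.1 rem is wrong by a known amount.* The totals above depend on assumed doses and on full CT at each visit. The third biopsy is optional and the MRI alternative is allowed throughout.
- *Patients are told the wrong figure.* The consent pages are not available, and they may already give a yearly figure.
- *Sites would stop scanning at 7.* Section 12.5.1.6 describes risk and is not a stopping rule. Section 6.3 and Appendix A govern scan timing.

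**Conclusion.** The point holds for the scan count. The stated maximum of 7 equals the routine count at week 48 and is passed at the next scheduled visit under either interval: week 56, or about week 60 to 64. By two years the count is 11 to 14. This needs no assumption beyond a patient remaining progression-free without new therapy.

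The rem part is conditional. About 14 to 20 rem at 11 to 14 scans rests on the assumed split of 10.1 rem, three biopsies and a full CT at every visit. It shows the likely scale and does not correct the stated figure.

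This is a quantified safety statement contradicted by the plan's own schedule. The efficacy analyses do not use it and are unaffected.

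**What to change.** - Restate section 12.5.1.6 as first-year exposure: 7 scheduled scans, plus any off-schedule confirmatory scan, plus NaF PET/CT where used.
- Add the yearly exposure for patients who continue treatment.
- Recalculate the rem from the actual dose of each procedure, and show those doses.
- Reconcile section 6.3 with Appendix A, footnote 8, on the imaging interval after one year.
- Clarify whether the calendar intends a CT at the end-of-treatment visit, and include it in the figure if so.
- Check that the consent form agrees with the revised section.

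The cost is one recalculation and an amendment to the wording. The downside is a less favourable stated exposure.
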